Full Protocol

**Retrospective Analysis of the Use of Biologics for Juvenile Idiopathic
Arthritis Related Uveitis in Abou El Reesh Pediatric Hospital, Cairo
University**

Background and introduction

Juvenile Idiopathic Arthritis (JIA) remains, globally, the most common systemic disorder associated with pediatric uveitis. It accounts for approximately 75% of cases of pediatric anterior uveitis (AU) and affects around 30% of ANA positive JIA patients (regardless their type of arthritis).¹ In a cohort study from the Cairo University Pediatric Hospital, JIA accounted for 39% of all cases of pediatric uveitis (unpublished data).

The uveitis, being asymptomatic, chronic and often severe, leads to complications in a large number of patients. Studies estimate that 28–67% of patients with JIA-associated uveitis develop ocular complications, with 12% developing poor visual outcome. The main causes of poor vision were cataract, band keratopathy and macular edema.²

The only means of improving long term effects of uveitis, is early and aggressive anti-inflammatory treatment.³

The main line of treatment of non-infectious causes of uveitis have been topical and systemic corticosteroids. However, it is well known that their prolonged use often leads to ocular and systemic complications, especially in the pediatric age group.⁴

In 2019, the American College of Rheumatology/Arthritis Foundation recommended that in severe active chronic AU or in the presence of sight-threatening complications, methotrexate (MTX) and a monoclonal antibody TNFi should be administered immediately. This is recommended over MTX as monotherapy. They also recommended that inadequate response to one monoclonal TNFi at standard JIA dose, the dose and or frequency should be increased rather than switching to another monoclonal antibody TNFi.⁵

Immunosuppressive drugs are used as steroid-sparing agents but are not free of complications. They increase the susceptibility of children to infection, may cause organ toxicity, reversible bone marrow suppression and may possibly lead to the development of malignancies.³

Thus, our study aims to analyze the use of biologics in our hospital (Abou el Reesh, Cairo University) for children with JIA in controlling their ocular inflammation, prevention of the development of sight threatening complications and if this outweighs their potential associated side effects.

Patients and methods

Population of study & disease condition

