Retrograde analysis of data of all patients presented to Aboul Reesh uveitis clinic taking biologics from January 2017- January 2020. In our hospital, the rationale for using biologics was a high frequency of sight-threatening, frequent recurrences of uveitis or intolerance to steroids or other immunosuppressive drugs, with severe adverse reactions.

Sample size:

It is expected to review 250 patients files of Aboul Reesh uveitis clinic to find all JIA patients with ocular inflammation treated with biologics.

Inclusion criteria

1. Both genders
2. Age up to 16 years
3. Diagnosed JIA according to rheumatological criteria with ocular affection
 - Any type of arthritis (oligoarticular, polyarticular, systemic onset, ocular JIA)
 - ANA positive or negative
4. Uncontrolled uveitis or frequent relapses

Exclusion criteria:

1. Patients without definitive diagnosis as JIA

2. JIA patients on biologics without ocular affection (for systemic control) or with uveitis controlled without the use of biologics
4. Patients without adequate duration for follow-up (less than 3 months) or lost follow up data
5. Patients without available data prior to the start biologics (to compare control of the uveitis)

Methodology

Data will be obtained from by retrospective analysis of all files of patients with JIA from the Abou El Reesh ophthalmology outpatient clinic.

The patients with ocular inflammation treated by biologics will be further analyzed.

The data analyzed will divided into pre and post biologic treatment:

In both we will document-

-Baseline BCVA (in logMar notation)

- Grading of ocular inflammation

(Anterior chamber and vitreous cells were graded as +0.5, +1, +2, +3 and +4 according to the guidelines of the Standardization of Uveitis Nomenclature Working Group)

- Number of relapses in one year

- Development of sight threatening complication

- Dose and frequency of systemic, regional and topical steroids

- Other interventions required

Treatment parameters to be analyzed include type, duration and dose of biologic agent used, time taken to reach inflammation control, adverse effects, and time taken to develop those adverse effects.

Improvement or worsening of activity of inflammation was assessed according to the Standardization of Uveitis Nomenclature Group's directions (2 step improvement or worsening of cells/flare)

Treatment was determined as efficacious if one of the following was fulfilled:

1. No relapses or decrease in the number of relapses

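### Adverse effects are listed only as a biologic treatment parameter, not in both periods, so relief of earlier drug toxicity cannot be shown directly and attribution to the biologic is uncertain

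*Combined protocol and SAP*

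**What the plan says.** The study aim, at the end of Background and introduction, is to examine how well biologics control ocular inflammation and prevent sight-threatening complications, and "if this outweighs their potential associated side effects". The same section says of corticosteroids that "their prolonged use often leads to ocular and systemic complications, especially in the pediatric age group", and it lists infection, organ toxicity and marrow suppression among the risks of immunosuppressants.

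Under Population of study & disease condition, one of the hospital's reasons for using a biologic is "intolerance to steroids or other immunosuppressive drugs, with severe adverse reactions".

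Methodology sets up the comparison: "The data analyzed will divided into pre and post biologic treatment". Six items follow for both periods: visual acuity, inflammation grade, relapses in a year, "Development of sight threatening complication", "Dose and frequency of systemic, regional and topical steroids" and "Other interventions required". A separate sentence on treatment parameters covers the type, duration and dose of the biologic and then "time taken to reach inflammation control, adverse effects, and time taken to develop those adverse effects".

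Exclusion criterion 5 removes children with no data from before the biologic. The only purpose it gives for those data is comparing control of the uveitis. The Statistical analysis plan names no analysis of adverse effects.

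**The concern.** The two sides of the weighing are measured differently. Benefit rests on a within-child comparison of two periods; adverse effects are listed for one period only. The document itself says that the earlier drugs are often toxic and that toxicity is sometimes why a biologic is started. For such children, relief of that toxicity is an obvious possible benefit, yet no item records it directly.

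Attribution is also affected. Steroid dose is documented in both periods, so the plan allows for steroids continuing after the biologic starts. Without a record of what was present beforehand and which drugs were in use at the time, an event seen on the biologic cannot be reliably sorted into one that is new, one that was already there, or one due to a continuing drug.

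**Working it through.** The plan states no adverse-effect figure, so there is none to reproduce. The check sets the two Methodology lists against the aim and asks what each item can say about drug toxicity.

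| Item | Before | After | Bearing on drug toxicity |
|---|---|---|---|
| Visual acuity | yes | yes | none specific |
| Inflammation grade | yes | yes | none |
| Relapses in a year | yes | yes | none |
| Sight-threatening complications | yes | yes | may capture some ocular steroid harm |
| Steroid dose and frequency | yes | yes | exposure, not harm |
| Other interventions | yes | yes | content undefined |
| Immunosuppressant exposure | not named | not named | missing, unless placed under other interventions |
| Adverse effects and time to develop them | not listed | yes | the only direct item |

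Three things follow.

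1. **Benefit side.** The efficacy criteria concern relapses, steroid dose and visual acuity. All three have a record in both periods, so a change can be computed.
2. **Risk side.** Let p_post be the share of children with an adverse effect after the biologic, and p_pre the share in a comparable earlier period. The change is p_post - p_pre. Since p_pre is not collected, it can lie anywhere from 0 to 1, so the change lies between p_post - 1 and p_post.
3. **Attribution.** Time to develop an event suggests that events starting on the biologic are meant, but no rule says so and no baseline list exists to check it against. Onset time alone also does not separate the biologic from a drug given alongside it.

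Ranges for the change, with assumed values of p_post:

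| Assumed p_post | Lowest change (p_post - 100%) | Highest change (p_post - 0%) |
|---|---|---|
| 10% | -90 points | +10 points |
| 20% | -80 points | +20 points |
| 40% | -60 points | +40 points |

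With p_post assumed at 25%:

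- p_pre = 10%: 25% - 10% = +15 points.
- p_pre = 50%: 25% - 50% = -25 points.

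The planned data would report 25% in both cases. These percentages are illustrations, not estimates. They show only that the direction of change is not identified by the items listed.

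**The case against.** The strongest objection is about the aim. The side effects it refers to are most naturally those of the biologics, and these are collected with their timing. Net change in total drug toxicity is neither a stated objective nor an efficacy criterion. This stands: a plain account of the biologics' side effects remains possible, and relief of earlier toxicity is implied by the rationale rather than promised as an endpoint.

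A reader might infer that the plan counts every event after the start against the biologic, including toxicity carried over from other drugs. The document does not say that. It gives no attribution rule, and the onset wording fits new events better. The supportable statement is that attribution is unspecified.

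A reader might also infer that the risk side has no comparator and that earlier toxicity is never counted. That too goes beyond the text. Steroid dose and sight-threatening complications are recorded in both periods, and a steroid reduction counts as efficacy. These are proxies: they do not reach systemic steroid toxicity or immunosuppressant toxicity.

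The group started for intolerance may be smaller than the rationale suggests. Inclusion criterion 4 requires uncontrolled uveitis or frequent relapses, and exclusion criterion 2 removes uveitis controlled without biologics. A child started for intolerance alone, with controlled uveitis, appears ineligible. Children with both problems remain.

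Finally, the remedy has limits. Where toxicity prompted the switch, the earlier period is selected for events, so a before-and-after comparison would tend to favour the biologic. The files come from an ophthalmology clinic and may chart systemic events poorly. Both limits stand; they restrict what may be claimed but do not remove the case for recording the data.

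**Conclusion.** The point holds in limited form. Adverse effects are absent from the items documented in both periods, and nothing elsewhere provides for them before the biologic. The biologics' side effects can be described. Relief of earlier systemic steroid or immunosuppressant toxicity cannot be shown directly, and attribution of later events is uncertain because baseline events and concurrent immunosuppressants are not recorded as such.

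The size is unknown, since the plan gives no rates. Under the assumed figures, the same observed result is compatible with a rise of 15 points or a fall of 25. The reading assumes that the open-ended list of treatment parameters does not silently cover the earlier period and that the undefined item on other interventions does not systematically capture immunosuppressants. This is a cheap improvement to the risk side of the study; it does not invalidate the efficacy comparison.

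**What to change.** - Where charted, add two items to the list for both periods: adverse effects (date, type, seriousness and drugs in use at the time) and immunosuppressant exposure.
- Classify each event after the biologic as new or already present before it, and show the concurrent drugs.
- Report, for each period, events divided by child-years observed. This needs a stated pre-biologic window, which the plan does not define for adverse effects. Present the comparison as descriptive only.
- Split the table by whether intolerance was a reason for starting the biologic, because those children were selected for earlier events.
- Report how many children had no usable adverse-effect record from before the biologic.

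The cost is extra extraction and one more table. Exclusion criterion 5 already requires some pre-biologic data for every included child, though not necessarily on adverse effects. Systemic events will probably be under-charted in ophthalmology files, and the earlier period is partly selected for toxicity. The two biases may run in opposite directions, so the table supports no causal claim.

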2. Decrease in dose of topical or systemic steroids
3. Improvement of BCVA of at least two lines

Statistical analysis plan:

All data will be entered into Excel spreadsheets (Microsoft Corporation, Redmond, WA, USA). All statistical analyses will be performed using IBM SPSS version 22.0 software (IBM Corp., Armonk, NY, USA). Descriptive statistics will be summarized as the mean \pm standard deviation for numerical data, frequencies and percentages for categorical data. The ANOVA -test and Pearson moment correlation will be used to compare the means for the numerical data and to identify correlations between them. Chi-square test will be used to compare categorical data. P-values ≤ 0.05 will be considered statistically significant.

References

- 2) Qian Y, and Nisha R. (2010) Juvenile Idiopathic Arthritis Associated Uveitis. *Curr Opin Ophthalmol.* 21(6): 468–472. doi:10.1097/ICU.0b013e32833eab83

Retrospective Analysis of the Use of Biologics for Juvenile Idiopathic Arthritis Related Uveitis in Abou El Reesh Pediatric Hospital, Cairo University

First version, 1st march 2020

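### The efficacy rule is met by any one of three criteria, has no condition against worsening, and uses neither graded activity nor sight-threatening complications, so it can misclassify patients in both directions

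*Combined protocol and SAP*

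**What the plan says.** The Background and introduction sets the aim: to examine whether biologics control ocular inflammation and prevent sight-threatening complications, weighed against their side effects.

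The Methodology section lists what is documented in both the pre-biologic and the post-biologic period. The list includes graded inflammation ("Anterior chamber and vitreous cells were graded as +0.5, +1, +2, +3 and +4"), complications ("Development of sight threatening complication") and steroids by route ("Dose and frequency of systemic, regional and topical steroids"). It then adopts a standard for change in activity: "2 step improvement or worsening of cells/flare".

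The efficacy rule follows directly: "Treatment was determined as efficacious if one of the following was fulfilled". Its three criteria are:

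- Criterion 1, on relapses: "No relapses or decrease in the number of relapses"
- Criterion 2, on steroid exposure: "Decrease in dose of topical or systemic steroids"
- Criterion 3, on vision: "Improvement of BCVA of at least two lines"

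The Statistical analysis plan names no primary outcome. It does not say how activity change or complications bear on the efficacy label, or that they are reported beside it.

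**The concern.** The rule is the plan's only stated standard of success, and it does not line up with the aim.

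Meeting one criterion is enough, whatever happens on the other two or on outcomes outside the rule. Criterion 2 sets no minimum fall in dose and does not require the other routes to stay level. The 2-step activity standard is defined immediately before the rule and then not used in it. Complications are recorded but also play no part.

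At stake is what the success proportion means. Read alone, it does not show how many of the patients counted as successes had worse inflammation, lost vision or developed a new complication. Nor does it show how many of the others had a clear improvement in inflammation.

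**Working it through.** The plan gives no response rate to reproduce, so the check applies the rule as written to constructed patients. On the listed grades (+0.5, +1, +2, +3, +4), a change between +1 and +3 is two steps, which meets the plan's own standard in either direction.

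| | Patient A | Patient B |
|---|---|---|
| Cells | +1 to +3 (two steps worse) | +3 to +1 (two steps better) |
| Sight-threatening complication | new | none |
| Relapses | non-zero, not fewer | non-zero, not fewer |
| Topical dose | lower | unchanged |
| Systemic dose | unchanged | unchanged |
| BCVA | gain under two lines | gain of one line |
| Criterion 1 met | no | no |
| Criterion 2 met | yes | no |
| Criterion 3 met | no | no |
| Label | efficacious | not efficacious |

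Patient A worsens on both outcomes named in the aim and is a success. Patient B improves on one, worsens on neither, and is not.

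**Zero relapses.** Take Patient B again, but with no relapses before or after the biologic. Criterion 1 is now met, because its first limb asks only for no relapses, so the label becomes efficacious. The same holds for a patient with zero relapses in both periods whose cells do not change at all. Patient B's result therefore depends on a relapse count that is non-zero and not lower.

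**Direction of error.** Let S be the number labelled efficacious, a the number of those who worsened on activity, BCVA or complications, and b the number not labelled who had a 2-step improvement in activity and none of those worsenings. A rule that removed the first group and added the second would count S − a + b, a change of b − a. The documents give neither a nor b, so neither the sign nor the size of b − a is known.

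**Room to worsen.** On the listed grades, a site at +3 can rise by one step only and a site at +4 cannot rise. Neither can show a 2-step worsening in cells at that site. Because anterior chamber and vitreous cells are graded separately and the change standard also mentions flare, an eye at its ceiling at one site may still worsen at another.

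**The case against.** The strongest reply is that the plan already handles much of this. Activity grade, relapses, complications and steroids by route are all documented before and after the biologic, and the Statistical analysis plan provides frequencies and percentages for categorical data. Separate results could be produced without any change to the text. That is fair as far as it goes: the data are planned for, and the reader who sees only one proportion is a possibility rather than a certainty. But the efficacy label still uses neither outcome, and nothing commits the report to showing them with it.

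A second reply is that relapse count is itself partly a measure of inflammation. This stands. The inflammation aim is not wholly absent from the rule; what is absent is graded activity. Relapses also do not protect the label, because criterion 2 or 3 alone is enough even when relapses increase.

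A third is that a new complication may come from earlier disease or steroid exposure rather than from failure of the biologic. The Background itself says that prolonged steroid use often leads to ocular complications. The same applies to loss of BCVA, since the Background lists complications such as cataract and band keratopathy among the main causes of poor vision. This bears on how a no-worsening condition should be presented. It is not a reason to leave worsening unseen.

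Two stronger readings go too far:

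- A reader might infer that a patient whose only gain is reduced inflammation can never count as a success. The zero-relapse case shows otherwise.
- A reader might infer that the rule inflates the success proportion. Ignoring worsening can only raise it, but ignoring activity improvement can only lower it, and the documents do not show which effect is larger. Counting the possible combinations of outcomes would not settle this, because combinations are not patient frequencies.

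**Conclusion.** The concern holds in limited form. Applied as written, the rule can label a patient efficacious who worsened on both outcomes named in the aim. It can also deny the label to a patient with a 2-step improvement in activity, provided relapses are non-zero and not fewer, steroid doses are not lower and the BCVA gain is under two lines.

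This rests on the wording alone and needs no assumed rates. The net size and direction of the misclassification cannot be estimated from the documents, and no figure should be attached to it. The point should be fixed, but it does not undermine the study: the data needed are already listed for both periods, so the repair lies in the analysis and reporting.

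**What to change.** 1. Name three outcomes tied to the aim: 2-step improvement in activity, 2-step worsening in activity, and new sight-threatening complications. Report them beside the efficacy label and cross-tabulate them with it. This makes visible both the labelled patients who worsened and the unlabelled patients who improved. The second group includes Patient B, whose label item 3 does not change.
2. Report each of the three criteria separately. Show steroid change by route (topical, regional, systemic), so that a fall in one with a rise in another can be seen. Show patients with zero relapses both before and after as their own group.
3. Report the composite as written, and again with a no-worsening condition: no 2-step worsening of activity, no BCVA loss of two or more lines (mirroring criterion 3), and no sight-threatening complication first recorded after the biologic was started. The plan names no visit at which the rule is judged, so state one post-biologic assessment point for activity and BCVA, for example the last recorded visit. State also how two eyes are combined, for example that worsening in either eye counts.
4. As a sensitivity analysis, show the no-worsening composite using activity worsening alone, because both new complications and BCVA loss may reflect earlier disease or steroid exposure.
5. Report how many eyes and sites were already graded too high to worsen by two steps, separately for anterior chamber cells and vitreous cells.

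The cost is slightly more analysis of data already listed, plus two conventions that must be written down (assessment point and eye rule). The success proportion under the no-worsening version can only stay the same or fall.

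### The steroid criterion sets no date, size or duration for the decrease, so a fall from a flare-time dose can count as efficacy and the no-effect success rate is uncontrolled

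*Combined protocol and SAP*

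**What the plan says.** The combined protocol and SAP defines efficacy at the end of Methodology: "Treatment was determined as efficacious if one of the following was fulfilled". The three criteria are "No relapses or decrease in the number of relapses", "Decrease in dose of topical or systemic steroids" and "Improvement of BCVA of at least two lines". They are not ranked, and none is tied to a visit.

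The data behind them are described a little earlier: "The data analyzed will divided into pre and post biologic treatment". In each period the files supply, among other items, "Dose and frequency of systemic, regional and topical steroids" and "Number of relapses in one year". Relapses thus have a stated window; steroid dose does not. The lengths of the two periods are not given. The Statistical analysis plan section lists general tests and adds nothing on how a steroid decrease is to be established.

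Three other statements bear on the point. Inclusion criterion 4 requires uveitis that is not controlled or that relapses often. The exclusion criteria remove children with under 3 months of follow-up but set no common assessment time. The Background says: "The main line of treatment of non-infectious causes of uveitis have been topical and systemic corticosteroids".

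**The concern.** Children are selected in a bad phase of a fluctuating disease whose main treatment is steroids, so the dose near the start of the biologic is likely to be raised for many of them. A raised dose tends to come down later whatever is given next. With no comparison group, nothing in the design separates that fall from a drug effect.

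The open wording adds to this in four ways:

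- The abstractor must choose which pre-biologic dose and which post-biologic dose to compare, and the choice can decide the result.
- Any size of decrease counts, and it need not last.
- Topical and systemic doses are joined by an or, so a fall in one can count while the other rises.
- If any later lower dose is accepted, a longer record gives more chances to succeed. The review window is January 2017 to January 2020, so records could run from 3 months to at most about 3 years.

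Because one criterion suffices, the steroid item alone can carry the headline efficacy rate.

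**Working it through.** **Plan's own figure.** There is none to reproduce. The 250 in the Sample size section is a count of files to screen. The plan gives no dose distribution, visit schedule or expected success rate, so every rate below rests on assumptions.

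**Assumed model, no drug effect.** Monthly visits; four ordered dose levels occupied 20%, 40%, 25% and 15% of the time; a stationary latent severity with month-to-month correlation 0.5 to 0.95; 200,000 simulated children. *High start* means the biologic begins in a month at one of the two upper levels.

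**Step 1: start dose against one later visit.** A limit follows by hand. When the visits are far enough apart to be unrelated:

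- High start: the third level makes up 25/40 = 0.625 of starts and the fourth 15/40 = 0.375. The chance of being lower later is 0.625 × 0.60 + 0.375 × 0.85 = 0.375 + 0.319 = 0.69.
- Unrestricted start: 0.40 × 0.20 + 0.25 × 0.60 + 0.15 × 0.85 = 0.080 + 0.150 + 0.128 = 0.36.

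With correlation 0.5 to 0.95 and a high start, simulation at a single 6- or 12-month visit gives about 41-70%.

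**Step 2: any later lower dose counts.**

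| Start dose | Correlation | By 3 months | By 6 months | By 12 months |
|---|---|---|---|---|
| High | 0.5-0.9 | 54-85% | 72-97% | 88-99.8% |
| High | 0.95 | 41% | 58% | 76% |
| Unrestricted | 0.5-0.9 | 33-51% | 45-64% | 58-73% |

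Extending the unrestricted row to correlation 0.95 gives 25-51% by 3 months and 49-73% by 12 months. Its ceiling is 100% − 20% = 80%, because children at the lowest level cannot fall. With a high start and correlation 0.5 to 0.9, among children scored a success within 12 months, 63-84% were back at or above their start dose at a later visit in that year. A separate set-up (three or five dose levels, other visit counts, correlation 0.3 to 0.95, start at the top level) spans 30% to nearly 100%.

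**Step 3: equal windows, start month left out.** High start, correlation 0.5 to 0.9:

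- 12 months each side: about 47-48% lower, 47-48% higher, 4-5% tied.
- 3 months each side: 39-44% in each direction.

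This balance follows from the model: a stationary process conditioned only on the start month looks the same in both directions. Inclusion criterion 4 also selects on earlier history. Adding an assumed condition, at least 6 of the 12 prior months at the upper levels, the 12-month comparison gives about 57-74% lower against 21-36% higher (correlation 0.5 to 0.95), still with no drug effect.

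**Step 4: the composite.** If the criteria were independent, the chance of meeting at least one is 1 − (1 − s)(1 − r)(1 − v). Assume no-effect rates of s = 0.2 to 0.4 for steroids on fixed dates without a high start, r = 0.4 to 0.6 for relapses and v = 0.05 to 0.2 for visual acuity.

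- Low end: 1 − 0.8 × 0.6 × 0.95 = 0.544.
- High end: 1 − 0.6 × 0.4 × 0.8 = 0.808.

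So about 54-81% remain classed as efficacious after the steroid dates are fixed.

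**The case against.** The strongest reply is that the plan divides the data into a pre and a post period and records dose in both, so a period-to-period or last-visit comparison is as natural a reading as a search through all later visits. That stands. A reader might infer that, as written, any later lower dose counts however brief; the text leaves this open and does not say it. The omission remains, and Step 1 shows that even a sensible single-visit reading gives a high no-effect rate from a raised start dose.

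A reader might also infer that nearly every child would be called a success. The documents do not support that. It needs a high start dose, acceptance of any later visit, many visits and doses that are not strongly correlated. The Population section gives steroid intolerance as one reason for using biologics, and such children may have little or no dose left to reduce.

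Three further inferences go too far:

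- Loss of response is not invisible in the study: relapses after the biologic and worsening of inflammation are recorded. It is simply not scored in an any-one-of-three rule.
- Equal windows are not neutral once entry depends on earlier history (Step 3).
- The missing dates are not the only cause: the any-one rule, the absence of a minimum decrease and the lack of controls contribute too (Step 4).

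**Conclusion.** The concern holds in a limited form. Criterion 2 has no reference date, assessment date, minimum size or duration, in an uncontrolled cohort selected for active or relapsing disease, and it is sufficient alone for efficacy. Regression from a flare-time dose can meet it, and the plan does nothing to bound how often.

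The gap matters under either reading of the text, but the ranges in Steps 1 and 2 are illustrations, not estimates for this clinic. They depend on the assumed visit spacing, dose levels, correlation and start dose, none of which the documents give. What holds across the high-start models is that the no-effect rate is substantial and, if any later visit counts, rises with length of follow-up.

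This should be corrected before the files are analysed. The correction makes the measure interpretable, but it does not turn a before-and-after comparison into evidence of drug effect.

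**What to change.** Rewrite criterion 2 and its analysis as follows:

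- Compare mean dose over equal windows before and after the biologic, leaving out the start visit. Use one common window length (for example 6 or 12 months) for the main analysis, and report children with shorter records (at least 3 months) separately.
- Analyse topical and systemic doses separately, and count a decrease only if neither rises.
- Report the numbers with decrease, increase and no change, the mean change with a 95% CI, and the number whose dose later returns to the pre-biologic level.
- Report criterion 2 separately from the relapse and visual acuity criteria.
- State that equal windows reduce but do not remove regression to the mean, because entry selects on pre-biologic history, so the result cannot be attributed to the drug alone.

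The cost is a few sentences in the plan and some extra extraction of dated doses from files already under review. The efficacy rate will probably look less favourable.

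### A steroid reduction made for tolerability can be scored as efficacy, because criterion 2 is sufficient alone and is not tied to inflammation

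*Combined protocol and SAP*

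**What the plan says.** All references are to the combined protocol and SAP.

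- **Why biologics were given** (Population of study & disease condition): the reasons listed include "frequent recurrences of uveitis or intolerance to steroids or other immunosuppressive drugs, with severe adverse reactions".
- **Who is analysed** (Inclusion criteria, item 4): "Uncontrolled uveitis or frequent relapses". The Exclusion criteria remove children "with uveitis controlled without the use of biologics".
- **Efficacy rule** (end of Methodology): "Treatment was determined as efficacious if one of the following was fulfilled". The three items are "No relapses or decrease in the number of relapses", "Decrease in dose of topical or systemic steroids" and "Improvement of BCVA of at least two lines".
- **Inflammation** (Methodology): cells are graded by SUN before and after the biologic, and change is judged by "2 step improvement or worsening of cells/flare". This measure is not among the three efficacy items and does not qualify any of them.
- **Steroid data** (Methodology): dose and frequency by systemic, regional and topical route are recorded for both periods. No date or window is given for the pre-biologic dose. Neither the indication for the biologic nor the reason for a steroid change is on the extraction list.

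**The concern.** The Background states the aim as finding out whether biologics control ocular inflammation and prevent sight-threatening complications. A lower steroid dose supports that aim when the eye stays quiet on less steroid. It does not when the steroid was reduced because the child could not tolerate it.

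The plan names intolerance as a reason for starting the drug and then accepts the likely consequence of intolerance as sufficient proof of success. For these children the outcome is mixed up with the indication. This is not regression to the mean in relapse counts, which concerns criterion 1, and a longer baseline period would not remove it. The comparison is before versus after in treated children only, so no untreated group would show how often steroid doses fall for tolerability alone. What is at stake is the meaning of the proportion scored efficacious.

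**Working it through.** The documents give no expected success rate, no share of steroid-intolerant children and no power calculation, so there is no planned figure to reproduce. The 250 under Sample size is a count of files to review. The check is therefore a reading of the rule, followed by an illustration on assumed values.

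**Step 1: apply the rule to one child.** Take a child with active uveitis and severe adverse reactions to systemic steroid.

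1. The child is eligible, because the uveitis is uncontrolled.
2. A biologic is started and the systemic steroid is reduced because of the adverse reactions.
3. Suppose the SUN grade is unchanged or higher, relapses are not fewer and BCVA has not improved.
4. Criteria 1 and 3 fail. Criterion 2 is met, and one criterion is enough, so the child is scored efficacious.

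Read literally, criterion 2 is also met if the systemic dose falls while topical use rises. Regional steroid is recorded but does not appear in the criterion, so a change of route can also score.

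**Step 2: size.** Define:

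- s = share of analysed children who are steroid-intolerant
- p = probability of success by any other route
- q = probability that the recorded dose falls for tolerability alone after the pre-biologic measurement, in an intolerant child

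Assuming independence, recorded success = p + (1 − p)·s·q, so inflation = s·(1 − p)·q.

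All three inputs are assumptions. The ranges used are s = 10–40%, p = 20–80% and q = 0–1.

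| s | p | q | Inflation = s(1 − p)q |
|---|---|---|---|
| any | any | 0 | 0 points |
| 0.10 | 0.80 | 0.5 | 0.10 × 0.20 × 0.5 = 1 point |
| 0.40 | 0.80 | 1 | 0.40 × 0.20 × 1 = 8 points |
| 0.10 | 0.20 | 1 | 0.10 × 0.80 × 1 = 8 points |
| 0.40 | 0.20 | 0.5 | 0.40 × 0.80 × 0.5 = 16 points |
| 0.40 | 0.20 | 1 | 0.40 × 0.80 × 1 = 32 points |

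A mid-range case: with s = 0.30 and p = 0.30, recorded success is 0.30 + 0.70 × 0.30 × q. That is 40.5% at q = 0.5, 46.8% at q = 0.8 and 51% at q = 1, against 30% without tolerability-driven reductions.

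**Step 3: what drives the range.** The term q depends on when the pre-biologic dose is read. If the steroid had already been stopped by then, no later fall can be recorded and q = 0. The plan does not fix that date. A lenient criterion 1, which accepts any fall in relapses, would push p up and the inflation down.

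**The case against.** A reader might infer that steroid-intolerant children are successes by virtue of their indication, whatever the biologic does. The documents do not support that, for three reasons.

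- It would need a recorded dose fall after baseline in every such child (q = 1). A child already off steroids at the pre-biologic measurement can never meet criterion 2, which works in the opposite direction.
- Entry still requires uncontrolled uveitis or frequent relapses, so intolerance alone does not bring a child into the analysis. In active disease the steroid dose may stay the same or rise if the biologic fails, so the drug's effect still influences criterion 2.
- The stated reason covers intolerance to steroids or to other immunosuppressants. Intolerance to the latter alone implies no steroid reduction.

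These points stand and limit the claim to what can happen. They do not remove it: active disease together with a poorly tolerated steroid is exactly the case in Step 1.

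It can also be said that steroid sparing is a benefit in itself, given the harms of prolonged use described in the Background, and that inflammation is analysed separately. Both are true. Steroid sparing on a quiet eye should count, but criterion 2 does not ask for a quiet eye, and the separate SUN assessment does not enter the efficacy label.

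Finally, a reader might infer that the error could never be repaired. In a retrospective chart review the missing items can still be extracted later if the files hold them. Doing so before the analysis is simply cleaner.

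**Conclusion.** The concern holds in limited form. Under the stated rule, a steroid reduction made for tolerability is scored as efficacy even when uveitis is unchanged or worse, and the design has no comparison that would expose this. That follows from the text and needs no assumed numbers.

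The size cannot be determined from the documents. On the assumed ranges in the working, with independence, it is 0 to 32 percentage points. The upper end requires a 40% share of intolerant children, all with a recorded fall, and only 20% succeeding otherwise. It should not be read as an expected value, and zero is possible. The efficacy definition should be changed before analysis.

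**What to change.** 1. In the efficacy definition, count a steroid decrease only when the SUN grade at the lower dose is controlled, or at least not worse than before the biologic. State in advance what counts as controlled and as not worse. This uses grades the plan already collects, applies to every child whatever the indication, and needs no judgement of motive from old notes.
2. Fix one reference date for the pre-biologic steroid dose and apply it to all files.
3. Extract the indication for the biologic from the same files, with an unknown category. Separate intolerance to steroids from intolerance to other immunosuppressants.
4. Report each of the three criteria separately, as well as the combined result, and show them by indication.

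Criterion 2 should not be barred for all steroid-intolerant children. That would discard real steroid sparing in children whose eyes are quiet on less steroid.

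The cost is one extra extracted field, a reworded criterion and probably a somewhat lower headline success rate. Some children will fall in the unknown category where the notes are silent on indication.
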